7.4.4.2 Withdrawal Period

ECG data will be summarized by presenting descriptive statistics of observed values, change from baseline, and changes from withdrawal baseline by visit and treatment.

7.4.5 Vital Signs, Weight, and BMI

7.4.5.1 Treatment Period

At each visit and endpoint, descriptive statistics (mean, SD etc.) will be provided by treatment group for

- Observed and change from baseline values of each vital sign parameter, including orthostatic changes in systolic blood pressure, diastolic blood pressure, and pulse rate;
- Observed and change, and percent change from baseline values in weight and BMI.

A similar MMRM model for the primary efficacy variable by using corresponding baseline will be applied for the following variables at the specified time points.

- Change and percent change from baseline in body weight (kg) at Weeks 1, 2, 3, 4, 6, 8, 10, and 12.
- Change and percent change from baseline in BMI at Weeks 1, 2, 3, 4, 6, 8, 10, and 12.

The number and percentage of subjects with Markedly Abnormal Post-baseline Vital Signs (MAPVS), defined in [Table 11.1](#), will be presented by visit, endpoint, or study period and by treatment group. Included are subjects having experienced at least once post-baseline MAPVS during the double-blind phase, up to and including endpoint.

Table 11.1: – Criteria for Markedly Abnormal Post-Baseline Vital Signs and Weight

Parameter (unit)	Markedly Low	Markedly High
SBP (supine, standing) (mmHg)	<90	≥180
	Value ≤ 90 and ≥ 20 decrease from baseline	Value ≥ 180 and ≥ 20 increase from baseline
DBP (supine, standing) (mmHg)	<50	≥105
	Value ≤ 50 and ≥ 15 decrease from baseline	Value ≥ 105 and ≥ 15 increase from baseline
Pulse rate (supine, standing) (bpm)	<50	≥120
	Value ≤ 50 and ≥ 15 decrease from	≥120 and increased >15 from

321

	baseline	baseline
Weight (kg)	≥ 7% decrease from baseline	≥ 7% increase from baseline
Temperature (°C)	N/A	Value ≥ 38.3°C and ≥0.8°C increase from baseline
Orthostatic Criteria		
SBP orthostatic criteria (mmHg)	≥ 20 mmHg reduction from supine to standing position	N/A
DBP orthostatic criteria (mmHg)	≥ 10 mmHg reduction from supine to standing position	N/A
Orthostatic tachycardia (bpm)	N/A	≥ 20 bpm increase from supine to standing position in pulse rate

BMI measurements will be used to classify a subject’s weight status as underweight, normal, overweight or obese using [Table 11.2](#) (Category 1) and as underweight/normal, overweight, obesity class I, obesity class II, and obesity class III using [Table 11.3 \(Category 2\)](#). Shifts from Baseline to Week 12 Endpoint will be produced by treatment group for the number and percentage of subjects that fall into each BMI category. In addition, the number and percentage of subjects with 3%, 5%, 7%, and 10% reduction in body weight will be presented by visit and treatment group for overall safety population as well as by baseline BMI groups (Category 2).

Table 11.2: – BMI Weight Status Category 1

BMI (kg/m ²)	Weight Status
< 18.5	Underweight
18.5 ≤ BMI < 25.0	Normal
25.0 ≤ BMI < 30	Overweight
≥ 30.0	Obese

Table 11.3: – BMI Weight Status Category 2

BMI (kg/m ²)	Weight Status
BMI < 25	Underweight/ Normal
25 ≤ BMI < 30	Overweight
30 ≤ BMI < 35	Obesity Class I
35 ≤ BMI < 40	Obesity Class II
40 ≤ BMI	Obesity Class III

A listing of subject data for those who satisfy MAPVS at least once post-baseline visit in the double-blind treatment period will be presented.

7.4.5.2 Withdrawal Period

Vital sign data will be summarized by presenting descriptive statistics of observed values, change from baseline, and changes from withdrawal baseline by visit and treatment.

7.4.6 Assessments of Withdrawal Effects (CSSA, DESS, HAM-A, and MADRS)

CSSA total score, DESS total score, MADRS total score, and HAM-A total score will be summarized by presenting descriptive statistics (N, mean, median, and range) of observed values and change from withdrawal baseline by treatment and visit (ie, both clinic and non-clinic visits) for the withdrawal period.

A similar analysis will be performed by gender as well.

7.4.7 Columbia Suicide Severity Rating Scale (C-SSRS)

According to FDA draft guidance for suicidal ideation and behavior ([7]), the following C-SSRS outcomes, which have binary responses (yes/no), will be re-ordered and numbered to facilitate the further definitions of the composite endpoint and comparative endpoint of C-SSRS as below.

Category 1 – Wish to be Dead

Category 2 – Non-specific Active Suicidal Thoughts

Category 3 – Active Suicidal Ideation with Any Methods (Not Plan) without Intent to Act

Category 4 – Active Suicidal Ideation with Some Intent to Act, without Specific Plan

Category 5 – Active Suicidal Ideation with Specific Plan and Intent

Category 6 – Preparatory Acts or Behavior

Category 7 – Aborted Attempt

Category 8 – Interrupted Attempt

Category 9 – Actual Attempt

Category 10 – Completed Suicide

Category 11– Self-injurious behavior without suicidal intent

Unless otherwise specified, C-SSRS table outputs will be presented by treatment for following analysis time points: lifetime (when applicable), baseline, any post-baseline in DB period, and any post-withdrawal Baseline. Definitions of these analysis time points are given in [Table 12](#). The analysis time point is applied to suicidal ideation score and ideation intensity total score.

Table 12: Definition of Analysis Timepoint

Analysis Timepoints	eCRF Visit(s) Used	C-SSRS Version	Derivation Rule
Baseline	Screening	1 month prior to screening	Most severe value
	Baseline	Since last visit	

321

Any post-baseline in DB period	Post-baseline visits up to and including Week 12/EOT	Since last visit	Most severe value
Any post- withdrawal Baseline visit	Post-withdrawal baseline visits up to and including Week15/EOS	Since last visit	Most severe value

At each analysis time points, the following binary variables will be derived.

- Any Suicidal Ideation (Categories 1-5)
- Any Suicidal Behavior (Categories 6-10)
- Any Suicidality (Categories 1-10)
- Individual Item for Category 6-11, respectively.

Comparative endpoints for ‘Emergence’ (outcomes that include events that first emerge) and ‘Worsen’ (outcomes that include events that worsen) will be derived as below. See [Table 13](#).

Table 13: Comparative Endpoint of C-SSRS in DB Treatment Period

Comparative Endpoints (Relative to DB Baseline)	Derivation Rule
Emergence of Suicidal Ideation	No suicidal ideation at Baseline, and any type of suicidal ideation in any post-baseline in DB period
Emergence of Serious Suicidal Ideation	No suicidal ideation at baseline, and any serious suicidal ideation [ideation score of 4 or 5] in any post-baseline in DB period
Emergence of Suicidal Behavior	No suicidal behavior at baseline, and any type of suicidal behavior in any post-baseline in DB period
Emergence of Suicidality	No suicidality at baseline, and any suicidality in any post-baseline in DB period
Worsening of Suicidal Ideation	Most severe suicidal ideation in any post-baseline in DB period is more severe than the most severe value at baseline

7.4.7.1 Treatment Period

The number and percentage of subjects with following categories will be summarized by treatment for lifetime, baseline and any post-baseline in DB period, respectively.

- each type of suicidal ideation,
- any suicidal ideation,
- each type of suicidal behavior,
- any suicidal behavior,
- any having self-injurious behavior without suicidal intent,
- any suicidality

321

At any post-baseline visit in DB period, comparisons between each dasotraline group and placebo group for suicidality will be conducted using Fisher's exact test.

In addition, the number and percentage of subjects with following categories will also be summarized by treatment for any post-baseline in DB period.

- emergence of suicidal ideation,
- emergence of serious suicidal ideation,
- worsening of suicidal ideation,
- emergence of suicidal behavior,
- emergence of suicidality

Shift from baseline to any post-baseline in DB period in suicidal ideation score will be presented by treatment to show the percentage of subjects with values 0 ('No ideation present') to 5 ('Active ideation with plan and intent'). Descriptive statistics (N, mean, standard deviation, median, and range) will be reported for Ideation intensity total score at baseline, each scheduled post-baseline time point, and endpoint for observed value as well as change from baseline. Data collected on actual suicide attempts (lethality of actual attempts and potential lethality of attempts) will be presented in a data listing.

All summaries pertaining to the C-SSRS will be based on subjects in the safety population.

7.4.7.2 Withdrawal Period

The number and percentage of subjects with following categories will be summarized by treatment for any post-withdrawal baseline for withdrawal population.

- each type of suicidal ideation,
- any suicidal ideation,
- each type of suicidal behavior,
- any suicidal behavior,
- any having self-injurious behavior without suicidal intent,
- any suicidality

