15.4.2.6. Columbia Suicide Severity Rating Scale (C-SSRS)

The number and percentage of subjects with suicidal ideation, suicidal behavior, emergence or worsening of suicidal ideation or suicidal behavior will be summarized by treatment for overall post-baseline treatment period and for the withdrawal period, separately. Shift from baseline to any post-baseline in the treatment period (worst case) in suicidal ideation score will be presented by treatment.

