During the study and prior to database lock, the treatment assignments for all subjects are provided to the Bioanalytical Contract Research Organization (CRO) to facilitate plasma PK sample handling and analysis. No PK samples are analyzed for placebo subjects.

Protocol and IRT Amendment for Stratification Factor of Region

For this US study, there is no concern of ‘region’ difference for treatment effect. Sponsor’s initial intention of including stratification factor of region was to provide an optimization approach to ensure a balanced treatment assignment within each region. It should be noted that stratification by region was not implemented in study SEP360-221, which is also a US study with a similar study design.

The study team noticed on July 20, 2017 that the stratification by region was not implemented as planned, ie, the initiated sites in IRT were linked to incorrect regions (See [Section 6.1.5.1](#) for details). As of July 20, 2017, among 50 planned sites of this study, a total of 44 sites were screening subjects; and 137 subjects from 35 sites had already been randomized. Due to the ‘random’ nature of the incorrect assignment of region according to the root cause of this incident, the study team decided to remove stratification criteria related to ‘region’ to minimize the impact of this mistake. Stratification criteria were amended in study protocol V3.00 and randomization is to be balanced using only permuted blocks with baseline number of binge eating days per

321

week (3 – 4 binge eating days per week, > 4 binge eating days per week).

4. Changes in Planned Analyses

There is not any change made in this SAP from the analyses planned in the protocol.

5. Efficacy and Safety Variables

[Section 6.1.2](#) provides definitions of DB Baseline and Withdrawal Baseline. For the sake of simplicity, hereafter, Baseline and DB Baseline will be used in an interchangeable way.

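### SAP 7.4.7.2 leaves out, without declaring it, the protocol's withdrawal-period summary of emergent or worsening suicidality on the C-SSRS

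*SAP*

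**What the plan says.** **Protocol 15.4.2.6** plans counts of subjects with ideation and with behavior, and adds that "emergence or worsening of suicidal ideation or suicidal behavior will be summarized by treatment for overall post-baseline treatment period and for the withdrawal period", each period separately. It does not say what withdrawal-period emergence is measured against.

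**SAP 7.4.7** sets up the variables.
- Table 12 defines the withdrawal time point as "Post-withdrawal baseline visits up to and including Week15/EOS" and takes the most severe value, with no comparison to an earlier value.
- Emergence and worsening are defined in one place, "Table 13: Comparative Endpoint of C-SSRS in DB Treatment Period". Every rule there compares a post-baseline double-blind value with the double-blind baseline.

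**SAP 7.4.7.1** (treatment period) lists six presence categories and then adds: "In addition, the number and percentage of subjects with following categories will also be summarized by treatment for any post-baseline in DB period". Five categories follow: emergence of ideation, of serious ideation, of behavior and of suicidality, and worsening of ideation.

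**SAP 7.4.7.2** (withdrawal period) says "The number and percentage of subjects with following categories will be summarized by treatment for any post-withdrawal baseline for withdrawal population". It repeats the six presence categories and stops.

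**SAP section 4** states: "There is not any change made in this SAP from the analyses planned in the protocol".

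**The concern.** A presence count answers whether a subject had ideation at any visit after withdrawal baseline. Emergence and worsening answer whether that ideation was new or more severe than before. The protocol asks for both in the withdrawal period; the SAP plans only the first.

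The difference matters because of who is in the table. The withdrawal population (SAP 6.1.9) includes subjects who stopped drug early and excludes completers who enter the extension. SAP 5.2.1 says that subjects with Type 4 or 5 ideation during the study will be discontinued. To the extent that this happens, subjects with on-treatment ideation pass into the withdrawal table, and their number may differ between arms. A difference between arms in presence could then reflect what happened on treatment and not what followed the last dose.

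**Working it through.** No figure in the documents needs recomputing. The check sets the texts side by side and then follows four hypothetical subjects through the rules.

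**1. Category count**

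| | Presence categories | Emergence or worsening categories |
|---|---|---|
| Protocol 15.4.2.6, treatment period | planned | planned |
| Protocol 15.4.2.6, withdrawal period | planned | planned |
| SAP 7.4.7.1, treatment period | 6 | 5 |
| SAP 7.4.7.2, withdrawal period | 6 | 0 |

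**2. Could another part of SAP 7.4.7 restore the missing cell?** Its introduction says that C-SSRS tables cover several time points, including post-withdrawal baseline, unless otherwise specified. Table 13 does specify otherwise: its title and every derivation rule are confined to the double-blind period. The binary variables derived at all time points are presence variables. Nothing restores the summary.

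**3. What the rules do with four hypothetical subjects.** All have no ideation at double-blind baseline. Scores are on the 0 to 5 ideation scale and are invented to trace the logic. The last three columns apply Table 13-type rules to the post-withdrawal-baseline visits; under such a rule, newly emergent ideation also counts as worsening.

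| Subject | On treatment | At Week 12/EOT | After last dose | SAP 7.4.7.2, any ideation | Emergent vs double-blind baseline | Emergent vs withdrawal baseline | Worse vs withdrawal baseline |
|---|---|---|---|---|---|---|---|
| A, carried over | 2 | 2 | 2 | counted | yes | no | no |
| B, new | 0 | 0 | 2 | counted | yes | yes | yes |
| C, worse | 2 | 2 | 4 | counted | yes | no | yes |
| D, resolved then returned | 3 at Week 1, then 0 | 0 | 3 | counted | yes | yes | yes |

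- Under SAP 7.4.7.2 all four count once as any ideation. The rows by type would show C's score of 4, but not that it had risen from 2.
- Against double-blind baseline, A and B are still alike. Carrying Table 13 over unchanged would not separate carried-over from new ideation.
- Against withdrawal baseline, A is separated from B, C and D.
- If the reference were the worst score at any time on treatment, D would be neither emergent nor worse, and a possible withdrawal effect would be hidden.

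**4. Which reference the documents already use.** Protocol 15.4.2 summarizes continuous withdrawal data as change from Week 12/EOT. SAP 7.4.1 uses change from withdrawal baseline, which Table 6.1 places at days -5 to 3 around the last dose for measures other than CSSA and DESS. Withdrawal baseline therefore matches the plan's own convention.

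**The case against.** The strongest case on the other side has four parts.

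1. **The information is not wholly lost.** Discontinuation-emergent adverse events are summarized by preferred term and by time since last dose (SAP 7.4.2). MADRS and CSSA totals, each of which includes a suicidality item, are summarized as change from withdrawal baseline (SAP 7.4.6). SAP 7.4.1 could give a change in the ideation score. All data are listed by subject (SAP 6.2.1), and with few cases a reader could sort carried-over from new by hand. This stands in part. A reader might infer that the trial cannot show whether new or worse suicidality follows stopping, and the documents do not support that. But adverse events depend on being reported as such, totals and mean changes are not counts of subjects, and listings are not summaries by treatment.

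2. **The SAP is not the sole cause.** The protocol names no reference for withdrawal-period emergence, so restoring its sentence would not by itself separate carried-over ideation. This is correct, and the fix must therefore name the reference.

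3. **The withdrawal objective does not rest on the C-SSRS.** Protocol 5.3 names CSSA, DESS, HAM-A and MADRS for that objective. The C-SSRS falls under general safety, and both the endpoint in Protocol 6.4 and the synopsis speak only of frequency and severity. This also stands: a reader should not infer that the withdrawal objective goes unassessed. The explicit plan in Protocol 15.4.2.6 is still unmet.

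4. **The stakes are modest.** The table is a descriptive safety summary. The one serious adverse event of suicidal ideation in SEP360-221 (Protocol 4.2) is reported without its arm or its timing relative to stopping drug, so it gives no size for a withdrawal effect.

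**Conclusion.** The point holds as an undeclared omission. The protocol plans withdrawal-period counts of emergent or worsening suicidality, the SAP neither defines nor tabulates them, and section 4 says that nothing changed. The withdrawal C-SSRS table therefore mixes carried-over with new or worse ideation, and the other planned outputs close that gap only partly.

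In size it is five comparative categories in one period and none in the other. How many subjects would be affected cannot be stated, because the documents give neither the size of the withdrawal population nor an expected rate of suicidality in it. Efficacy conclusions, type I error and data collection are untouched. It should be corrected, and the correction is cheap.

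The conclusion rests on reading Protocol 15.4.2.6 as applying its full list, including emergence and worsening, to both periods, which is what its sentence says.

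**What to change.** In SAP 7.4.7, add a withdrawal-baseline time point to Table 12 (the Week 12/EOT C-SSRS, consistent with Table 6.1 and Protocol 15.4.2) and a withdrawal counterpart to Table 13:

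- **Emergence** of ideation, serious ideation, behavior and suicidality: absent at withdrawal baseline and present at any post-withdrawal-baseline visit. For serious ideation, follow Table 13: no ideation at the reference, then a score of 4 or 5.
- **Worsening** of ideation and of behavior: most severe post-withdrawal-baseline category above that at withdrawal baseline. Behavior belongs here because the protocol's sentence covers it. Table 13 has no such row for the treatment period either, so the same row could be added there.

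Tabulate these by treatment in 7.4.7.2 for the withdrawal population, beside the presence counts. Optionally flag subjects with any earlier ideation at double-blind baseline or on treatment, so that a case like D is visible as a recurrence.

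Two details need a sentence each. SAP 6.1.2.4 allows no imputation of a missing withdrawal baseline, so say how subjects without one are classified and print their number. SAP 7.4.7.1 says that all C-SSRS summaries use the safety population, while 7.4.7.2 uses the withdrawal population; confine the former to the treatment period.

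If the sponsor prefers not to add the summary, section 4 should declare the omission and give the reason.

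The cost is SAP wording and a few descriptive table rows, from C-SSRS data already scheduled at Week 12/EOT and Weeks 13, 14 and 15.

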7.4.8 Other Safety Assessments

7.4.8.1 Breath Alcohol Test

The number and percentage of subjects at each assessment (negative/positive) will be summarized at each visit by treatment group.

7.4.8.2 Neurological Examination

Frequency distribution of each category of assessment (ie, Cranial Nerves, Motor System, sensory System, Reflexes, Coordination, Gait and Rhomberg's test) will be summarized by

treatment at each visit. A shift table of each assessment for baseline to the worst case during treatment period will also be presented by treatment.

7.4.8.3 Abuse Potential Monitoring Plan (APMP)

The Abuse Potential Monitoring Plan (APMP) for dasotraline has been designed to detect potential abuse of the compound and to more closely monitor AEs consistent with the pharmacology. The plan detects irregularities in the handling of dasotraline in clinical trials and identifies the misuse of dasotraline or other psychoactive substances. Moreover, the APMP provides a process by which events subject to additional monitoring are identified, processed, and reviewed. Events subject to additional monitoring are identified based on the pharmacology of dasotraline, as well as adverse event profiles of compounds with similar mechanisms of action.

APMP results will be provided by sites before DBL and provided in a listing.

7.4.8.3.1 Medication Handling Irregularities

Medication handling irregularities will be summarized using the following categories:

- Drug accounting errors, not involving suspected abuse or diversion by subject
- Non-compliance with study procedures, not involving suspected abuse or diversion by subject
- Other cases not involving suspected abuse or diversion by subject
- Suspected or known abuse or diversion of study drug
- Suspected abuse (nonmedical use) of alcohol, illicit substances, OTC drugs or prescription drugs obtained outside the study protocol

Instances that meet the threshold criteria for a medication handling irregularity will be summarized descriptively. Both the number of instances and the number (%) of subjects experiencing medical drug irregularities will be provided for each category and by treatment. Instances of medication handling irregularity will be listed for all randomized subjects.

7.4.8.3.2 Events Subject to Additional Monitoring (ESAMs)

In addition to monitoring for irregularities in medication handling, AEs that may be suggestive of a developing abuse potential, will receive special attention. The adverse experiences or related signs and symptoms that will require additional monitoring (ESAMs) are listed in [Attachment 9.6](#). AEs identified as ESAMs will be summarized by ESAM type and PT by treatment for safety population (treatment period) and withdrawal population (withdrawal period), respectively. ESAMs will also be listed for all randomized subjects.
